17.0 References

PROSPECTIVE EVALUATION OF CYBERKNIFE STEREOTACTIC RADIOSURGERY FOR LOW AND INTERMEDIATE RISK PROSTATE CANCER: HOMOGENOUS DOSE DISTRIBUTION

SCHEMA

^{*}Prescribed dose to PTV; prostate receives 8 Gy x 5

PATIENT POPULATION (see section 4.0 for complete eligibility)

Histologically-confirmed, adenocarcinoma of the prostate

Clinical Stage T1b - T2b, NX-0, MX-0

One of the following combinations:

- Gleason score 2-6 and PSA ≤ 20
- Gleason score 7 and PSA < 10

ECOG Performance Status 0-1

No prior prostate radiation or other definitive therapy

Required sample size: 319 patients.

ELIGIBILITY CHECKLIST

	Is there histologically proven prostate adenocarcinoma, biopsy within one year of enrollment?
(2-6)	What is the Gleason Score?
(T1b – T2b)	What is the clinical T-stage? (AJCC 6 th Edition)
(Y)	Is the patient clinical Nx or N0, and Mx or M0?
(0-20)	What is the patient's PSA?
	Does the patient fall into one of these risk groups (AJCC 6^{th} Edition): - Low: CS T1b-T2a, Gleason 2-6, PSA ≤ 10 - Intermediate: CS T2b, Gleason 2-6, PSA ≤ 10 , or CS T1b-T2b, and Gleason 2-6, PSA ≤ 20 ng/ml, or Gleason 7, PSA ≤ 10 ng/ml
(Y)	Is the prostate volume $\leq 100 \text{ cc}$?
(0-1)	What is the ECOG performance status?
(N)	Has the patient undergone prostatectomy or cryotherapy of the prostate?
(N)	Has the patient had radiotherapy to the prostate or lower pelvis?
	Has the patient implanted hardware near that would prohibit appropriate treatment planning or treatment delivery, in the investigator's opinion?
(N)	Has the patient had chemotherapy for a malignancy in the last 5 years?
` ,	Has the patient had an invasive malignancy (other than this prostate cancer, or basal or squamous skin cancers) in the last 5 years?
	Has the patient's androgen function been ablated during the past 2 months? See Section 5.12

ACCP001.4

1.0 BACKGROUND

- 1.1 Prostate cancer is the most common malignancy in men; an estimated 219,000 cases will be diagnosed in the United States in 2007¹. PSA screening has led to earlier stage diagnoses; in 1998, 92% of prostate cancers were diagnosed with clinically organ-confined disease². According to the NCI Consensus Conference in 1988³, and the Prostate Cancer Panel of the American Urological Association in 1995⁴, treatment options that should be discussed with each patient in this category include radical prostatectomy, external beam radiation therapy (RT), interstitial brachytherapy and watchful waiting.
- 1.2 First attempts to treat organ-confined prostate cancer with radiotherapy yielded poor biochemical disease free outcomes, as insufficient doses were delivered to the target. Since the 1980's, conformal RT techniques have been developed which reduced dose to the surrounding organs, allowing the safe delivery of greater doses to the prostate. Conformal RT has been achieved either through 3-dimension conformal external beam RT, or through prostate brachytherapy. These techniques have yielded disease-free outcomes similar to those seen with radical prostatectomy (see table 1), although not without toxicity.
- 1.3 Modern external beam radiotherapy uses three-dimensional treatment planning, delivering RT to the prostate through typically 5-7 coplanar beams. With intensity modulated radiotherapy (IMRT), dose is modulated through each of these beams. Due to variations in patient positioning and internal organ motion, the position of the prostate cannot be accurately determined using exterior skin marks. Placing gold fiducials in the prostate, and imaging prior to treatment deliver reduces targeting error, but this typically does not account for movement within a given treatment session. Such intrafractional movement can be substantial: in one study⁵ it was estimated at 2mm, 6mm, and 7mm in the left-right, anterior-posterior, and cranial-caudal directions, respectively. Radiation oncologists account for this uncertainty by adding a margin to the intended target. Expanding radial dimensions to create a "planning target volume" (PTV) increases the volume of surrounding normal structures in the high dose region, potentially increasing toxicity.
- 1.4 In the past decade, transperineal ultrasound-guided brachytherapy has gained popularity for treating organ-confined prostate cancer. Brachytherapy allows the delivery of conformal, high-dose radiotherapy to the prostate, with a rapid dose fall-off outside of the implanted region. Favorable long-term outcomes using permanent iodine-125 (I-125) and palladium-103 (Pd-103) implants have been reported in numerous studies^{6 7 8 9 10}.
- 1.5 High-dose rate (HDR) brachytherapy has been used in the treatment of prostate cancer since the 1980's 11 12 13 14 15 16 17 18 19 20 21 22 23. Catheters are placed temporarily in the prostate, and then loaded with a high-dose Iridium-192 source, delivering a few fractions of very high-dose RT. Initial protocols employing HDR combined conventionally fractionated external beam RT with an HDR boost. More recent reports have employed HDR as monotherapy 24 25 26 27 28 29. Adjusting for pre-treatment risk factors, these studies yield bDFS outcomes at least as favorable to those seen with LDR brachytherapy or conformal dose-escalated RT or IMRT (see table 1). Indeed, a prospective, non-randomized study from William Beaumont Hospital 30 comparing HDR monotherapy versus LDR brachytherapy (Pd-103) showed a superior 5-year event-free survival (98% vs. 85%, p=0.01) and a trend towards improved freedom from cancer failure (98% vs. 92%, p=0.1) in the HDR cohort. The same group showed acute and late toxicity, potency, and QOL following HDR brachytherapy was more favorable than either LDR brachytherapy or conformal external beam RT^{31 32}. The rate of impotence three years following HDR was 16%, compared to 45% following LDR brachytherapy.

Table 1. bDFS Outcomes for Low-Risk Prostate Cancer

				Median	5-yr bD	FS: Definit	ion	
Rx	Details	Institution	# pts	f/u yrs	Phoenix	ASTRO	Ave [‡]	
HDR	45-50Gy + 2-4 fx boost	Seattle, Kiel, Beaumt ³³	46	5		96%	92%	
прк	$36Gy + 5.5-6Gy \times 4 \text{ boost}$	CA Endocurie ³⁴	70	7.25	93%	90%	9270	
HDR	Monotx: 6–7.25Gy x 6	CA Endocurie ³⁵	117#	8		96%	97%	
IIDK	Monotx: 9.5Gy x 4	Beaumont ³⁶	95 [†]	4.2		98%	9/%	
LDR	Monotx: 145Gy I125	RTOG 9805 ³⁷ phase II	95	5.3	99%	93%	88%	
LDK	Monotx: I125 & Pd103	11 inst meta-analysis ³⁸	1444	5.25	86%	88%	0070	
	IMRT: 70Gy, 2.5Gy/fx	Clev Clin ³⁹ hypofract	36	5.5	97%	97%	97%	
	IMRT: 81Gy, 1.8Gy/fx	MSKCC ⁴⁰	203	7	92%	84%		
EB	3dRT/IMRT: >72Gy	9 instit meta-analysis ⁴¹	70	5.7		79%		
ED	3dRT/IMRT: 70-76Gy	9 instit meta-analysis ⁴²	231	6.3	94%		83%	
	3dConformal: 78Gy	MDA rand dose-esc ⁴³	32	>5	93%	92%		
	proton bst to 79.2Gy	MGH, Loma Linda ⁴⁴	116	5.5	96%	80.5%		
	Institutions	Author	#pts	f/u yrs	Definition	bDFS	Ave [‡]	
	Baylor	Hull ⁴⁵	299	3.9	PSA≥0.4	92.5%		
	ClevClinic &	Kupelian ⁴⁶	524*	5.5	PSA≥0.2	92%		
RP	MSKMercy	45	324	5.5	F3A≥0.2	9270	94%	
	Univ Pennsylvania	D'Amico ⁴⁷	322	5	ASTRO	88%		
	Hopkins	Han ⁴⁸	899 [*]	5.9	PSA≥0.2	98%		

*Number of patients, bDFS estimated based on proportions within each risk group. #75% low risk, 25% intermediate; †Included T2b in low-risk group. ‡Weighted average, using ASTRO or stated definition.

- Radiation oncologists fractionate RT dose to reduce toxicity to surrounding normal tissues. For most cancers, by delivering dose over several weeks, equivalent cancer-killing effect is achieved with reduced long-term toxicity. The effect of dose fractionation on both cancer and normal tissues can be estimated using the "linear-quadratic model". In this model, the alpha-beta ratio reflects the response of normal tissues or cancers to changes in RT dose per fraction. Most cancers respond to RT as do rapidly-dividing normal tissues (e.g., skin or mucous membranes), and thus have high α/β ratios, in the 10-12 Gy range. Tissues with lower α/β ratios are more sensitive to large dose per fraction (also known as hypofractionated) RT.
- 1.7 The favorable control rates observed with hypofractionated RT led radiobiologists to reconsider α/β ratio of prostate carcinoma. Several researchers have concluded that prostate cancer has an unusually low α/β ratio of about 1.5Gy⁴⁹ ⁵⁰ ⁵¹ ⁵² ⁵³. Another analysis⁵⁴ estimated the α/β ratio was between 3.1-3.9 Gy; a more recent study⁵⁵ of 3756 patients yielded a ratio between 2.6 and 3.7Gy. A low α/β ratio is consistent with other biologic properties of prostate cancer: an unusually long tumor doubling times⁵⁶, and a very low proportion of proliferating cells⁵⁷. Although the actual α/β ratio for prostate cancer is debated, the accepted range of 1–4 Gy appears to be similar to, or smaller than the α/β ratios for late effects in the surrounding normal tissues (3-5 Gy). Thus a therapeutic gain could be achieved by hypofractionation. Indeed, this approach should result in equivalent or improved cancer control with reduced toxicity⁵⁸ ⁵⁹ ⁶⁰.

- 1.8 In 1951, Lars Leksell, a Swedish neurosurgeon, first described radiosurgery: the use of converging beams of ionizing radiation to non-surgically ablate intracranial lesions. He later developed the "GammaKnife", which focuses 201 columnated Co-60 beams at a single isocenter. A metal frame was fixed to the patient's skull, providing both a reference for treatment, and a means to rigidly fix the skull. Another method of delivering stereotactic radiotherapy uses multiple isocentric arcs from a linear accelerator equipped with a small collimator; again the patient rigidly immobilized.
- 1.9 In the 1990s a novel device was developed at Stanford University for delivering stereotactic radiosurgery without the need for rigid immobilization. This device, called "CyberKnife", uses a lightweight x-band linear accelerator mounted on an industrial robot. The system uses a pair of amorphous silicon detectors to gather orthogonal fluoroscopic images of the patient. Bony landmarks or implanted fiducials near the target are continuously imaged, and the system's computer automatically makes adjustments to account for variations in set-up or patient movement. The target can be treated from about 1200 different directions, using coplanar or non-coplanar beams. The CyberKnife can treat static intra- and extra-cranial sites with sub-millimeter accuracy.
- 1.10 The CyberKnife should be an ideal device for treating prostate cancer because 1) targeting accuracy for static targets is excellent, with an error of about 1mm, 2) it can adjust for intra-fractional organ motion, reducing the volume of the target PTV and therefore the dose to surrounding organs, 3) by using over one-hundred non-conplanar beams, the dose gradient between the prostate and surrounding tissues may be superior to that achieved with conventional linear accelerators, and 4) the radiobiology of prostate cancer may favor large dose per fractions.
- 1.11 The feasibility of CyberKnife for treating localized prostate cancer was first described by King at Stanford University⁶¹. Their phase I protocol delivered 36.25Gy in 5 fractions of 7.25Gy. In a recent report⁶² of acute and 18-month late toxicity in 26 "low-risk" patients, no patient experienced grade 3 or 4 acute or late toxicity, and only one patient experienced a grade 2 late morbidity (urethral stricture). Toxicity was less than that reported in MD Anderson's external beam dose escalation trial. Mean PSA 18 months after treatment was 0.22ng/ml. Naples Community Hospital reported⁶³ a series of more than 70 low and intermediate risk patients treated with the CyberKnife. The prostate received 35Gy in 5 fractions of 7Gy each; acute toxicity was minimal.

Table 2: Hypofractionated RT Schedules2Gy/fx Equivalent Dose(All doses expressed in Gy)Assuming α/β ratio of:Institution/protocolDose/fx #fxs Total dose1.5Gy 3Gy 10Gy

Institution/protocol	Dose/fx	#fxs	Total dose	1.5Gy	3Gy	 10Gy
Naples CyberKnife	7	5	35	85	70	49.6
Stanford CyberKnife	7.25	5	36.25	90.6	74.3	52.1
Beaumont HDR*	9.5	4	38	119.4	95	61.8
Demanes HDR*	7.25	6	43.5	108.8	89.2	62.5
This protocol: GTV	8	5	40	108.6	88	60
RTOG 0415	2.5	28	70	80	77	72.9

^{*}Does not account for heterogeneity in HDR plans.

1.12 Calculation of Equivalent Doses. In this protocol, the linear quadratic formula is used to calculate equivalent doses. Three assumptions are made: 1) sublethal damage is completely repaired between fractions, 2) no repair of sublethal damage occurs during a given fraction,

- and 3) no repopulation occurs during the treatment course (i.e., there is no time factor). Equivalent dose at a specified dose/fx d, for an assumed α/β ratio r, is expressed as EQD_d (α/β =r).
- 1.13 Dose Selection. See table 2 for 2Gy/fx equivalent doses. The 5-year bDFS outcomes for HDR series and for hypofractionated EBRT are superior to those reported using conventionally fractionated 3D conformal or IMRT (see table 1). This suggests that an EQD₂ of 80 Gy or more may be required to achieve 5-year bDFS in the 96-98% range. At Stanford and Naples Community Hospital, toxicity following CyberKnife (7.25 Gy x 5 fractions, and 7 Gy x 5 fractions, respectively, both calculated 3-5mm from the prostate border) was minimal. In the Naples series, median PSA outcomes one year after treatment was 1.2ng/ml, somewhat greater than that reported in brachytherapy series, suggesting dose escalation beyond 7Gy x 5 would be beneficial. The Stanford CK protocol gave an EQ2 74.3 to 90.6Gy (for α/β ratios of 3Gy and 1.5Gy, respectively); PSA response was excellent, falling to an average of 0.22ng/ml at 18 months. This protocol thus uses the Stanford dose and PTV: 7.25Gy x 5 fractions prescribed to the PTV, defined as the prostate expanded 3mm posteriorly, and 5mm elsewhere. The rapid dose gradient achievable with CyberKnife allows the simultaneous delivery of a greater dose to the prostate (GTV). To deliver a BED approaching that prescribed in the HDR monotherapy series, 8Gy x 5 is prescribed to the prostate. Thus the PTV receives an EQD₂ of 74.3Gy (if $\alpha/\beta=3$), or an EQD₂ of 90.6Gy $(\alpha/\beta=1.5)$. The prostate receives an EQD₂ $(\alpha/\beta=3)$ of 88Gy, or 108.6Gy for $\alpha/\beta=1.5$.

2.0 OBJECTIVES

PRIMARY OBJECTIVES: The primary safety goal of this study is to estimate, in both low-risk and intermediate-risk cohorts, the rates of acute and late grade 3-5 gastrointestinal and genitourinary toxicity observed during the five years following CyberKnife SRS for prostate cancer. The primary efficacy goal is to document the rate of biochemical Disease-Free Survival (bDFS), Phoenix and ASTRO definitions, at 5 years.

SECONDARY OBJECTIVES: to measure the following in the study population: Rates of local failure, distant failure, disease-free survival, disease-specific survival, and overall survival; quality of life (QOL) in generic and organ-specific domains; work effort required in treatment planning and delivery of CyberKnife SRS.

Patients will be followed annually to 10 years, to collect additional data for descriptive analysis.

3.0 **DEVICE**

Accuray, Inc. (Sunnyvale, CA), received FDA clearance in July 1999 to provide treatment planning and image guided stereotactic radiosurgery and precision radiotherapy for lesions, tumors and conditions of the brain, base of skull and cervico-thoracic spine, head and neck using the CyberKnife. On August 10, 2001, Accuray, Inc. received 510(k) FDA clearance (510(k) number K011024) to provide treatment planning and image-guided stereotactic radiosurgery and precision radiotherapy for lesions, tumors, and conditions anywhere in the body when radiation treatment is indicated.

4.0 PRETREATMENT EVALUATION

Evaluations Required for Eligibility:

- 4.1 Complete history & physical examination
- 4.2 Assessment of performance status

- 4.3 Pathologic confirmation of adenocarcinoma of the prostate
- 4.4 Serum PSA, < 90 days prior to registration, or < 60 days prior to hormone therapy, and 30 or 90 days after discontinuing finasteride or dutasteride, respectively, See section 5.3.
- 4.5 CBC, platelets, serum BUN and creatinine and testosterone; may be drawn after registration
- 4.6 Ultrasound of prostate, or CT of pelvis or digital rectal exam (DRE)
 - 4.6.1 To determine prostate size by imaging: volume = $\pi/6$ x length x height x width; if volume determined by DRE estimate, must be confirmed on CT planning; if volume is > 100 cc then patient is ineligible
 - 4.6.2 Measurement from CT or ultrasound \leq 6 months prior to registration or \leq 14 days prior to registration if hormone therapy is given; it patient had taken finasteride or dutasteride, volume determined > 30 or > 90 days respectively after discontinuation
- 4.7 Patient should be able to complete questionnaires (see appendix VI); baseline questionnaires may be completed before or after enrollment, but before treatment.
 - 4.7.1 SF-12 questionnaire
 - 4.7.2 AUA questionnaire
 - 4.7.3 EPIC-26 questionnaire
 - 4.7.4 SHIM questionnaire
 - 4.7.5 Utilization of Sexual Medications/Devices questionnaire

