5.0 PATIENT SELECTION & ELIGIBILITY

- 5.1 Histologically proven prostate adenocarcinoma
 - 5.1.1 Gleason score 2-7 (reviewed by reference lab, see also section 5.4; if initial pathology differs from that of reference lab, the reference lab's interpretation will be used for eligibility and risk group assignment (see also section 7.2.1)
 - 5.1.2 Biopsy within one year of date of registration
- 5.2 Clinical stage T1b-T2b, N0-Nx, M0-Mx (AJCC 6th Edition)
 - 5.2.1 T-stage and N-stage determined by physical exam and available imaging studies (ultrasound, CT, and/or MRI; see section 4.5)
 - 5.2.2 M-stage determined by physical exam, CT or MRI. Bone scan not required unless clinical findings suggest possible osseous metastases.
- 5.3 PSA ≤ 20 ng/ml (see section 5.4; if pre-enrollment PSA was drawn > 60 days prior to CyberKnife treatment, another PSA obtained ≤ 60 days prior to treatment, will become the pre-treatment PSA and will determine eligibility and risk group; pre-treatment PSA must be drawn 30 or 90 days after discontinuing finasteride or dutasteride respectively)
- 5.4 Patients belonging in one of the following risk groups:
 - 5.4.1 Low: CS T1b-T2a and Gleason 2-6 and PSA \leq 10, or
 - 5.4.2 Intermediate: CS T2b and Gleason 2-6 and PSA \leq 10, or CS T1b-T2b, and Gleason 2-6 and PSA \leq 20 ng/ml, or Gleason 7 and PSA \leq 10 ng/ml
- 5.5 Prostate volume: ≤ 100 cc
 - 5.5.1 Determined using: volume = $\pi/6$ x length x height x width
 - 5.5.2 Measurement from CT or ultrasound \leq 6 months prior to registration.
- 5.6 ECOG performance status 0-1
- 5.7 No prior prostatectomy or cryotherapy of the prostate
- 5.8 No prior radiotherapy to the prostate or lower pelvis
- 5.9 No implanted hardware or other material that would prohibit appropriate treatment planning or treatment delivery, in the investigator's opinion.
- 5.10 No chemotherapy for a malignancy in the last 5 years.

- 5.11 No history of an invasive malignancy (other than this prostate cancer, or basal or squamous skin cancers) in the last 5 years.
- 5.12 No hormone ablation for two months prior to enrollment, or during treatment. This includes LHRH agonists (e.g. leuprolide, goserelin, triptorelin), antagonists (e.g. degarelix), peripheral blockers (e.g. flutamide, bicalutamide, nilutamide), estrogens (e.g. DES), bilateral orchiectomy and 5-alpha reductase inhibitors (finesteride or dutasteride).
- 5.13 Completion of patient questionnaires in section 4.7.
- 5.14 Consent signed.

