- 6.2 PATIENT REGISTRATION: Patients may be registered only after all eligibility criteria are met: see Eligibility Checklist above, and Inclusion Criteria and Exclusion Criteria CRFs (Case Report Forms). After the patient signs the Consent Form the patient is enrolled in the study, and scheduled for treatment. The pre-treatment CRFs are then filled out by the investigator and/or research assistant. This data is retained in the patient's chart and in research office. The date of registration shall be the date the consent was signed. Fiducials must be placed within 60 days, and the first fraction of radiosurgery must be administered within 90 days of registrations.

7.0 **PATHOLOGY**

- 7.1 Pathology Evaluation: Slides/blocks from the pre-treatment diagnostic prostatic biopsy will be reviewed to confirm the diagnosis and Gleason score. Other histopathologic features, including extent of tumor in the biopsies, the number of biopsies positive and perineural invasion, shall be recorded.
- 7.2 Central Review: All consenting patients must have a complete representative set of biopsy slides or tissue block submitted to the Central Pathology Laboratory in order for the case to be evaluated for central pathology review. The following must be provided:
 - 7.2.1 A complete representative set of biopsy slides or tissue block; if initial pathology differs from that of reference lab, the reference lab's interpretation will be used for eligibility and risk group assignment
 - 7.2.2 A Pathology report documenting the submitted blocks, core or slides contain tumor; the report must include the Accuray protocol number and the patient's case number. The patient's name and/or other identifying information should be removed from the report.
 - 7.2.3 Submit materials for central review to Bostwick Laboratory; other central review lab may be used if approved by Sponsor and Principal Investigator.

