8.0 TREATMENT: CYBERKNIFE RADIOSURGERY

- 8.1 FIDUCIAL PLACEMENT: All patients will have gold fiducial seeds measuring 3-5 mm placed in the prostate prior to treatment planning. At least four fiducial seeds will be placed under transrectal ultrasound guidance, using either transperineal or transrectal approach, with local anesthesia and/or sedation as required. The use of linked fiducials are encouraged, since they may migrate less than individually placed fiducials. The physician will place seeds such that they are visible (and not superimposed) on CyberKnife orthogonal imaging, are not collinear, and ideally are separated by 2cm or more. Fiducials will be placed as an outpatient procedure; at least three seeds must be usable for tracking during treatment. If an interim analysis shows unacceptable fiducial migration with a specific technique or type of fiducial, further use of this technique or type of fiducial may be prohibited by the Principal Investigator.
- 8.2 TREATMENT PLANNING IMAGING: The treatment plan will be created based on the risk group assigned by the reference lab review.
 - 8.2.1 To allow fiducial stabilization and resolution of swelling, planning studies will be imaged 5-10 days after fiducial placement. Alpha Cradle or a similar immobilization device will be used as needed. To avoid prostate distortion, in the

- primary CT used for treatment planning, no indwelling catheter shall be placed. If required to visualize the urethra, a catheter may be placed for the secondary imaging study only. CT scans will be taken for treatment planning. CT slices will be 1-1.5mm, with 200-300 slices taken centered approximately at the prostate. The imaging sets will be downloaded to the CyberKnife treatment planning system to develop the radiosurgery treatment plan.
- 8.2.2 If not medically contraindicated, all patients will undergo MRI imaging to determine the anatomical borders of the prostate, and if possible, the urethra. This study will be fused to the treatment planning CT. No endorectal coil allowed.
- 8.2.3 URETHRAL IDENTIFICATION: To record DVH data for the prostatic and membranous urethra, visualization of these structures is recommended, but not manditory. If the urethra cannot be visualized and contoured, then to insure the prostatic urethra meets the dose constraint specified in 8.3.4.7, the prescription dose of 36.25Gy shall be no less than 75% of Dmax. To identify the urethra, the following may be employed:

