9.0 PATIENT ASSESSMENTS AND TOXICITY

	Pre- entry	Follow-up interval: months post therapy						Years post therapy		
Assessment		day 5	1 wk	1	3	6	12	18	24 (every 6 mo up to 5 years)	6-10
History	X			X	X	X	X	X	Xb	
Physical exam (DRE)	X				X	X	X	X	Xb	
ECOG Performance Scale	X				X	X	X	X	Xb	
Prostate Biopsy & Gleason score ^a	X								X	
PSA	X				X	X	X	X	Xb	X
Prostate volume assessment	X									
CBC, platelets	X									
BUN, creatinine	X									
Testosterone	X			X	X	X	X	X	X^{c}	X^{c}
Toxicity evaluation	X	X	X	X	X	X	X	X	X^{b}	X
AUA score	X	X	X	X	X	X	X	X	X*	X
SF-12	X			X		X	X		X*	
EPIC-26 Questionnaire	X			X		X	X		X*	X
SHIM Questionnaire	X			X		X	X		X*	X
Utilization of Sexual Rx/Devices	X			X		X	X		X*	
a. Central review of path	ology; bio	psy recon	mend	led a	at 2	yrs,	& re	equir	red at time of failure	_

	110 01 001
b. Continue every 6 months through to year 5	
c. Testosterone levels will be monitored until the 24 month follow-up visit and will be optionally measured at follow-up visits out to 10 years.	
* Continue every 12 months through year 5;	

- 9.1 EVALUATION DURING TREATMENT & FOLLOWING TREATMENT
 - 9.1.1 PRE-ENTRY ASSESSMENT: see section 4.7.
 - 9.1.2 Stereotactic radiosurgery is an outpatient procedure. Patient management immediately after the procedure will follow routine patient care guidelines as determined by the physician. Subjects will be provided instructions on who to call with specific contact information, in the event they experience any untoward effects following treatment. In the event a subject experiences any untoward effects following CyberKnife treatment, information specific to the patient's condition and symptoms, treatment intervention required, and hospital stay and course will be recorded for purposes of clinical evaluation.
 - 9.1.3 ACUTE ASSESSMENT: Patients will have toxicity evaluation and AUA score on the last day of treatment.

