11.4.2 SECONDARY ENDPOINTS

- 11.4.2.1 QUALITY OF LIFE ASSESSMENTS: The SF-12 scores. AUA score, EPIC-26 scores are used to quantify quality of life (QoL) at baseline and repeatedly during the post treatment period (see Section 9.0). We will use the generalized estimating equation (GEE) method to provide valid inferences. This method was originated to make inference about average behaviour, where the dependent variable depends not only on the "explanatory" variable (time measured in months) but also on the correlation of a patient's repeated measurements. The GEE approach fits the model to the observed data as closely as possible, weighting each patients' "cluster" of measurements over time inversely to its variance – covariance matrix. With this method, no imputations are required and all data recorded is use in the analysis. Other important features of GEE are that no distributional assumptions for the dependent variable are required to use the method and in most cases valid inferences are provided even when the correlation structure is miss-specified. For each score, we will use GEE to fit a model to patients' longitudinal course of repeated values. We hypothesize that immediately following treatment, the GU & GI subsections of the EPIC-26 and the AUA will demonstrate a worsening of GU and GI function, but this will return to normal with time. We further hypothesize that the sexual function subset of the EPIC-26 will show gradual worsening function relative to baseline over the five-year follow-up period. These QOL outcomes will be compared to those reported in other prospective studies using the same instruments, including RTOG 0232 and 0415
- 11.4.2.2 ADVERSE EVENTS: All adverse events will be recorded on the case report forms. For both acute (<=90 days of treatment start) and late (>90 days of treatment start), the frequency and proportion of each type of adverse event will be presented in tabular form, on both a per-patient and a per-event basis.

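### Baseline quality-of-life forms may be completed after the fiducial implant, so acute urinary and bowel worsening may be understated, and section 4.7 conflicts with 5.13, 6.2 and the schedule

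*Combined protocol and SAP*

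**What the plan says.** Section 4.7 lists five baseline instruments (SF-12, AUA, EPIC-26, SHIM and the sexual medications/devices form) and sets one outer limit on their timing: "baseline questionnaires may be completed before or after enrollment, but before treatment".

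Other places point to an earlier time:

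- Section 5.13 makes "Completion of patient questionnaires in section 4.7" an eligibility item.
- Section 6.2 says "Patients may be registered only after all eligibility criteria are met", and dates registration at the signing of consent.
- The section 9.0 schedule puts all five forms in a pre-entry column, but section 9.1.1 reads only "PRE-ENTRY ASSESSMENT: see section 4.7".

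On what happens between registration and radiosurgery:

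- Section 6.2: "Fiducials must be placed within 60 days, and the first fraction of radiosurgery must be administered within 90 days of registrations".
- Section 8.1: "At least four fiducial seeds will be placed under transrectal ultrasound guidance, using either transperineal or transrectal approach". This applies to all patients and comes before planning.
- Section 8.2.1: "To allow fiducial stabilization and resolution of swelling, planning studies will be imaged 5-10 days after fiducial placement".
- Sections 8.2.1 and 8.2.3 allow a urinary catheter for a secondary planning scan. It is optional in general. It is required for the first 3 cases where MRI is used to identify the urethra.

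Section 11.4.2.1 models the AUA, EPIC-26 and SF-12 scores over time with GEE. It expects that, just after treatment, the urinary and bowel scores "will demonstrate a worsening of GU and GI function, but this will return to normal with time". It expects sexual function to decline gradually from baseline. Nothing there takes account of whether a baseline form came before or after the implant.

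**The concern.** A baseline should describe the patient before the trial procedures begin. Section 4.7 allows it to be taken after needles have been passed into the prostate and, in some men, after a catheter has been in the urethra. EPIC-26 asks about burning and bleeding on urination, bloody stools and rectal pain. These are symptoms that such procedures could plausibly cause.

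If the baseline is worse for that reason, the measured acute worsening is smaller than the true one and recovery to baseline is reached more easily. Both errors favour the device. The trial has a single treatment and no concurrent control, so nothing cancels a shifted baseline, and section 11.4.2.1 plans to compare the results with other prospective studies. The shift could also differ between sites, depending on when each hands out the forms.

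The conflict between 4.7 and the eligibility and registration rules adds to this, because two sites could follow the protocol and collect baselines at different points.

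**Working it through.** The quality-of-life endpoints have no stated sample size, standard deviation or success threshold, so there is no plan figure to reproduce. The check has three parts.

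**1. Is a post-implant baseline permitted?**

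- Section 4.7 expressly allows completion after enrollment. Section 6.2 dates registration at consent and places the implant up to 60 days, and the first fraction up to 90 days, after it. For every man the implant lies inside the permitted window.
- Planning imaging follows the implant, so any catheterised scan also lies inside the window.
- Sections 5.13, 6.2 and the pre-entry column point to completion before registration. But 5.13 and 9.1.1 both refer back to 4.7. The passages conflict, and the stricter ones do not override the permission.

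**2. Does the recall period reach back to the implant?**

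- AUA asks about roughly the past month. Most SF-12 items and most EPIC-26 items cover 4 weeks. (The itemised EPIC-26 bowel question prints no period of its own; the overall bowel question after it uses 4 weeks.) SHIM covers 6 months.
- A form completed at planning imaging, 5 to 10 days after the implant, has 5/28 = 18% to 10/28 = 36% of a 28-day window after the implant.
- With a 28 to 30 day window, the implant stays within recall for a further 28 − 10 = 18 to 30 − 5 = 25 days after imaging.
- It drops out only if the form is completed more than about 4 weeks after the implant. The 60- and 90-day limits allow that for some men.

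**3. How large could the bias be?**

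Let f be the share of men with a post-implant baseline and d the mean points that the procedure adds to their baseline score. Then

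bias in mean change from baseline = f × d.

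The documents give neither f nor d. Both are assumed below, in AUA points. Percentages are the share hidden of an assumed true mean worsening of 6 points.

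| f | d = 1 | d = 2 | d = 4 |
|---|---|---|---|
| 25% | 0.25 (4%) | 0.5 (8%) | 1 (17%) |
| 50% | 0.5 (8%) | 1 (17%) | 2 (33%) |
| 100% | 1 (17%) | 2 (33%) | 4 (67%) |

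The middle case is 0.5 × 2 = 1 point, and 1/6 = 17%. If the true worsening were 4 points, the corners would be 0.25/4 = 6% and 4/4 = 100%. If it were 10 points, they would be 0.25/10 = 2.5% and 4/10 = 40%. With all forms before the implant, f = 0 and this bias is zero.

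**The case against.** **The wording may already exclude late forms.** Treatment is not defined, and fiducial placement sits under the section 8.0 treatment heading, so 4.7 could be read as requiring forms before the implant. This reading is possible. But section 5.3 speaks of CyberKnife treatment, section 9.1.3 of the last day of treatment, and 8.1 describes the implant as coming before planning. If the sponsor intends the broader meaning, one sentence would settle it.

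**The documents do not show that the implant changes scores.** This stands. The wait in 8.2.1 concerns seed stability and swelling before imaging, not symptoms, and 14.4 lists only rare infection as a fiducial risk. The mechanism is plausible, but its size is not documented.

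**A post-implant baseline could be said to isolate the radiation effect.** The plan does not claim this, does not fix the baseline there, and in 14.2 counts fiducial risks among the risks of the study.

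**A pre-implant form is not perfectly clean.** Section 5.1.2 allows a biopsy at any time within a year of registration, so its effects may fall within recall. This stands, and the fix does not remove it.

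**Stronger readings a reader might infer.**

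- *That about half of a 6-point AUA rise would vanish, because three items each shift by one category.* For the group mean this needs every man to have a late baseline and to be fully affected (f = 100%, d = 3, 3/6 = 50%). The documents support neither.
- *That the share of the recall window after the implant measures the share of the score affected.* It does not.
- *That every man has a catheterised scan.* Most need not.
- *That all quality-of-life results are compromised.* A shifted baseline alters one time point; follow-up values to year 5 are as recorded. Only the sexual-function hypothesis names baseline explicitly; the urinary and bowel one speaks of a return to normal.

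**Conclusion.** The point holds in a limited form. Section 4.7 permits baseline forms after the fiducial implant and, in some men, after a catheterised scan, and it conflicts with 5.13, 6.2 and the pre-entry column. With recall of about 4 weeks and no control group, late forms may understate acute urinary and bowel worsening on the AUA and EPIC-26, and may affect the SF-12. The direction favours the device.

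The size is unknown. The range of 0.25 to 4 AUA points rests on assumed shares of 25% to 100% and assumed effects of 1 to 4 points; it illustrates the formula and is not an estimate. SHIM is little exposed because of its longer recall, and 11.4.2.1 does not list it for modelling. The primary toxicity and bDFS endpoints are not affected, and the sample size of 319 does not rest on quality of life. Confidence is high in the conflict and the permission, and lower in any material bias. The change is worth making because it costs so little.

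**What to change.** **Remaining patients.** State in 4.7 that all five baseline forms are completed after consent and before fiducial placement, and before any catheterised scan. Align 5.13, 6.2 and 9.1.1 with that rule. Because 6.2 dates registration at consent, 5.13 could be reworded as a requirement to be met before the implant. This also removes the need to decide what the word treatment covers.

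**Men already enrolled.** Compare the baseline form date with the implant date, and report how many forms are dated on or after the implant; this gives f. Repeat the quality-of-life models without those forms and show both results. Since planning scans follow the implant, the same check covers catheterised scans. The printed AUA, EPIC-26, SHIM and sexual-aids forms have a date field. The printed SF-12 does not, so use its CRF or visit date. The CRFs are held outside the documents, so confirm that the implant date is recorded there.

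**Cost.** One sentence in 4.7, the matching edits and a date check. There are no extra forms or visits and no change in sample size. A few late forms become protocol deviations, and the sensitivity analysis has fewer men and so less precision.
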